9.3 Level of significance and the power of the clinical investigation

Significance level is set to 0.05, Power to 80%.

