- Zou, G. (2011). Confidence interval estimation for the Bland-Altman limits of agreement with multiple observations per individual. *Stat Methods Med Res, S.* 0 (0): 1-13.

Addendum to Clinical Investigation Plan: A prospective, open-label, multicenter clinical investigation to assess the safety and performance of ARGOS-IO system in patients with Primary Open Angle Glaucoma (POAG)

To Current Revision: ARGOS-02_CIP_RevC_20140218

Part 1: Enrollment

Page 8, Table: Synopsis, Row: Study Design:

RevC

This clinical investigation prospective, open-label, multicenter, single-arm clinical investigation will be conducted in two stages using a Simon two-stage design. Subjects will be enrolled as follows:

First stage: 11 patients

Second stage: 11 patients

An interim analysis will be performed when the 11 patients of the first stage have completed their 3 month follow-up visits. The trial will be stopped if 2 or more patients have experienced a serious adverse device events (SADE) at this time. Otherwise enrollment will be resumed and the trial continued until an additional 11 patients have been enrolled in stage 2 and received ARGOS-IO implants. A conclusion for safety will be made if in total no more than 2 of the total of 22 patients experience an SADE.

Ammended

This prospective, open-label, multicenter, single-arm clinical investigation will enroll 22 consecutive Patients.

Enrollment will be temporarily halted in case a serious adverse device effect (SADE) occurs, and a Data and safety Monitoring Board (DSMB; see section "Safety Monitoring" on page 16) meeting will be conducted as soon as possible. The DSMB will then recommend whether to further continue the study as planned, or whether enrollment shall be stopped. A conclusion for safety will be made if in total no more than 2 of the total of 22 patients experience an SADE.

Page 8, Table: Synopsis, Row: Sample Size Considerations:

RevC

The primary aim of this study is to show "safety", which will be evaluated based on the percentage of subjects who experience an SADE (= "non-safety"), as defined in the primary endpoints.

For the study as a whole, "safety" will be determined based on the following decision rule: if in stage 1 the non-safety event rate is greater than 25%, the trial will be stopped (type 1 error rate of 0.05). If

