The trial will be conducted as an open, prospective, multicenter single-arm clinical trial using the two- stage design described by Simon (Simon, 1989). In the first stage, 11 patients will have an ARGOS-IO pressure sensor implanted, after which enrollment will be halted until the patients have completed their 3 months follow-up visits and an interim analysis has been performed. The interim analysis will be reviewed by the DSMB. If two or more of these 11 patients in the first stage are found to have had an SADE, further enrollment into the study will be stopped. If not, enrollment will resume until another 11 patients have had an ARGOS-IO pressure sensor implanted. If two or fewer of the total 22 patients experience an SADE, a conclusion for safety will made at the 5% significance level. A corresponding 95% confidence interval for the SADE rate will be calculated according to the procedure of Koyoma (2008).

All patients who receive an ARGOS-IO implant will return for 10 follow-up visits to the clinic (day 1, 3, 10, 30, 60, 90, 120, 180, 240, 360) during the 12-month post-surgical period (see Table 6: Assessment Schedule). To allow comparison of the IOP measurement methods, IOP measurements will be made at every visit with GAT and with the ARGOS-IO systems beginning at V5 (day 30).

Ammended

The trial will be conducted as an open, prospective, multicenter single-arm clinical trial. All 22 patients will be enrolled consecutively, until a SADE occurs. In that case, the DSMB will be called, and decides whether the enrollment can be continued or not. If two or fewer of the total 22 patients experience an SADE, a conclusion for safety will made at the 5% significance level. A corresponding 95% confidence interval for the SADE rate will be calculated according to the procedure of Koyoma (2008).

All patients who receive an ARGOS-IO implant will return for 10 follow-up visits to the clinic (day 1, 3, 10, 30, 60, 90, 120, 180, 240, 360) during the 12-month post-surgical period (see Table 6: Assessment Schedule). To allow comparison of the IOP measurement methods, IOP measurements will be made at every visit with GAT and with the ARGOS-IO systems beginning at V5 (day 30).

Page 66, 8.3.3.1 Study stopping rules:

RevC

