The primary purpose of this investigation is to assess safety of the investigational device. This will be judged statistically based on the number of individual patients experiencing serious device-related adverse events (SADEs). The study will be implemented in a two-stage design equivalent to the Simon optimum design to minimize the expected sample size (Simon, 1989). In the first stage, enrollment will be halted after 11 patients have received ARGOS-IO implants. An interim analysis will be conducted when these 11 patients have been followed-up for 3 months. If two or more patients experience SADEs in this time, the study will be stopped for safety reasons (Type I error rate = 0.05). If fewer than two have experienced SADEs, enrollment will be resumed and will be continued until a total of 22 patients have received ARGOS-IO implants. A final decision for safety will be drawn, if overall two or fewer of the total 22 patients have an SADE [SIMON optimum two stage design to minimize expected sample sizes, parameters: $\alpha=0.05$, $\beta=0.20$, $p_0 = 0.75$ (proportion in stage 1 without SADE), $p_1 = 0.94$ (proportion overall without SADE)]. A corresponding 95% confidence interval for the proportion of the safety population with SADEs will be calculated using the method proposed by Koyoma and Chen (2008).

Table 1. Study design

	First Stage	Overall
SADE-free Subjects		
Proportion	$p_0 = 0.75$	$p_1 = 0.94$
Minimum number required	10	20
Subjects with SADE		
Proportion	$1 - p_0 = 0.25$	$1 - p_1 = 0.06$
Maximum number allowed	1	2
Total Number of Subjects	11	22

Ammended

The primary purpose of this investigation is to assess safety of the investigational device. This will be judged statistically based on the number of individual patients experiencing serious device-related adverse events (SADEs). Patients will be enrolled consecutively until a total of 22 patients have received ARGOS-IO implants. A final decision for safety will be drawn, if overall two or fewer of the total 22 patients have an SADE [parameters: $p_1 = 0.94$ (proportion overall without SADE)]. A corresponding 95% confidence interval for the proportion of the safety population with SADEs will be calculated using the method proposed by Koyoma and Chen (2008).

Table 2. Study design

		Overall
SADE-free Subjects		
Proportion		$p_1 = 0.94$
Minimum number required		20
Subjects with SADE		
Proportion		$1 - p_1 = 0.06$
Maximum number allowed		2
Total Number of Subjects		22

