Page 87, 9.2 Sample Size Calculation:

RevC

The sample size calculation was based on the study's purpose of establishing safety.

To minimize the required sample size and consequently the number of patients exposed to risk while at the same time maximizing the chances of detecting safety events, a two-stage design based on the rate of non-events was chosen (Simon, 1989). The event of interest was defined as a serious device-related adverse events (SADEs). Based on a probability of non-events of $p_0=0.75$ for the first stage and an overall acceptable probability of $p_1=0.94$, a sample size of at least 11 evaluable patients in the first stage and additional 11 patients in the second stage are required. This maintains a type 1 error

probability of 5% and the power of 80% based on minimizing the maximal sample size and results in an expected sample size of 13.2 patients.

Ammended

The primary aim of this study is to show “safety”, which will be evaluated based on the percentage of subjects who experience an SADE (= “non-safety), as defined in the primary endpoints.

The study will be declared a success if the final non-safety event rate is less than 6% (type II error rate of 0.20) The calculation is based on a design optimizing the minimum expected sample size with parameters $\alpha=0.05$, $\beta=0.20$, $p_0=0.75$, $p_1=0.94$. According to Table 7, those parameters will be fulfilled if 2 or less SADE will occur in a sample of 22 patients.

Part 2: Interim Analysis

Page 16, Table: Synopsis, Row: Data Analysis and Statistics, Item: Interim Analysis:

RevC

An interim analysis to assess SADE will be performed, when the first 11 patients have completed the 3 month follow-up visit.

Ammended

An interim analysis to assess Safety and Performance will be performed, when the all patients have completed the 6 month follow-up visit or if an SADE occurs.

Page 87, 9.6 Interim Analysis:

RevC

One interim analysis is planned for this study. It will take place when all patients in the first stage have completed the first 3 months of the follow-up period and will determine whether or not to continue the study to the second stage based on the number of patients experiencing an SADE..

Ammended

An interim analysis is planned for this study. It will take place when all patients have completed 6 month follow-up period, or each time an SADE occurs, prior to the regular DSMB meeting

Part 3: Implant size selection

Page 74, 8.4.4.13 ARGOS-IO implant size assessment:

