2.5 Study Hypothesis

The specific hypothesis to be tested in this single arm two-stage design study is that the SADE rate is lower than 25%. It is expected that the observed SADE rate will be at most 6%. More precisely, let p be the true proportion of subjects with no SADEs, p_0 the proportion of subjects no SADE to be rejected and p_1 the expected proportion of patients overall without SADE. Then, the null hypothesis H_0 and the alternative hypothesis H_1 are:

$$H_0 = p \leq p_0 = 0.25 \quad \text{vs.} \quad H_1 = p > p_1 = 0.25.$$

If at most 2 SADE's occur in the 22 patients enrolled, a SADE rate lower than 25% can be concluded. This will be illustrated by the 95% confidence interval for the SADE rate which will be calculated using the method proposed by Koyama (Koyama & Chen, 2008). If the obtained

confidence interval does not include any value lower than 0.94, it can be concluded that the SADE rate is at most 6%.

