2.9 Sample Size Calculation

The primary aim of this study is to show “safety”, which will be evaluated based on the percentage of subjects who experience an SADE (= “non-safety), as defined in the primary endpoints.. To minimize the required sample size and consequently the number of patients exposed to risk while at the same time maximizing the chances of detecting safety events, the sample size calculation follows the principle of a two-stage design as proposed by Simon (Simon, 1989). The event of interest was defined as patients with at least one serious device related adverse event (SADE) in the 3 month period immediately following implantation. Based on a probability of non-events of $p_0=0.75$ for the first stage and an overall acceptable probability of $p_1=0.94$, a sample size of at least 11 evaluable patients in the first stage and additional 11 patients in the second stage are required. This maintains a type 1 error probability of 5% and the power of 80% based on minimizing the maximal sample size. Table 2 summarizes the consequences of the sample size calculation on the study design.

Table 2: Two-stage study design

	First Stage	Overall
SADE-free Patients		
Proportion	$p_0 = 0.75$	$p_1 = 0.94$
Minimum number required	10	20
Patients with SADE		
Proportion	$1 - p_0 = 0.25$	$1 - p_1 = 0.06$
Maximum number allowed	1	2
Total Number of Patients	11	22

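### The amended CIP claims a 5% level for 2 or fewer SADE patients in 22, but without the limit on the first 11 the type I error is up to 6.06%, and the SAP is unclear whether that limit binds the conclusion

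*Protocol*

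**What the plan says.** **Rev C.** CIP 9.1, 9.2 and Table 7 describe a Simon two-stage design with 11 + 11 patients. At most 1 SADE patient is allowed in the first 11 and at most 2 in all 22. Stated properties are alpha 0.05, power 80% and expected sample size 13.2. CIP 9.3 repeats the targets: "Significance level is set to 0.05, Power to 80" per cent.

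**Addendum to Rev C.** The amended text removes the two-stage structure. After a SADE the DSMB decides whether enrolment continues.
- Amended 8.1.1: "If two or fewer of the total 22 patients experience an SADE, a conclusion for safety will made at the 5% significance level".
- Amended 9.1: "A final decision for safety will be drawn, if overall two or fewer of the total 22 patients have an SADE". Its replacement design table has no first-stage column.
- Amended synopsis: "A conclusion for safety will be made if in total no more than 2 of the total of 22 patients experience an SADE".
- Amended 9.2, after restating alpha 0.05 and beta 0.20: "According to Table 7, those parameters will be fulfilled if 2 or less SADE will occur in a sample of 22 patients".
- Amended 8.1.1 and 9.1 keep the Koyama–Chen interval, which is a two-stage method.
- CIP 9.7, not among the amended sections supplied, still discontinues the study at more than 1 first-stage SADE patient.

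**SAP.**
- 2.5: "If at most 2 SADE's occur in the 22 patients enrolled, a SADE rate lower than 25% can be concluded". It calls the study two-stage but states no limit for the first 11.
- 2.1 places the 2-of-22 criterion and the 5% level directly after a rule terminating the trial at more than 1 SADE patient in the first 11. Sections 2.10 and 8.1 repeat that termination rule.
- 2.9, with Table 2 allowing at most 1 of 11 and 2 of 22: "This maintains a type 1 error probability of 5% and the power of 80% based on minimizing the maximal sample size".
- 7.2 bases the safety decision on Simon's two-stage rule.

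**The concern.** The final limit of 2 in 22 was derived jointly with the limit of 1 in the first 11. If the first limit goes and the second stays, the error rates change, yet the amended CIP carries the 5% over.

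The primary safety comparison is the only formal test (SAP 5.3). For one data pattern, 2 SADE patients in the first 11 and none afterwards, the documents support both a conclusion of safety at 5% and a failed trial. If that pattern counts as success, the level is exceeded and the two-stage interval no longer matches the rule.

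**Working it through.** **Inputs.** SADE rate to be ruled out: 1 − 0.75 = 0.25. Acceptable rate: 1 − 0.94 = 0.06 (CIP 9.2, SAP 2.9). Stages of 11 and 11, limits 1 of 11 and 2 of 22 (CIP Table 7, SAP Table 2). Assumptions: a one-sided test, as the direction of the conclusion implies; independent patients with a common rate q; all 22 evaluable.

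**1. The planned design, both limits.** With X1, X2 ~ Bin(11, q):

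P(success) = P(X1=0)·P(X2≤2) + P(X1=1)·P(X2≤1)

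- q = 0.25: 0.04224 × 0.45520 + 0.15486 × 0.19710 = 0.01923 + 0.03052 = **0.0497**
- q = 0.06: 0.50630 × 0.97524 + 0.35549 × 0.86178 = 0.49376 + 0.30635 = **0.8001**
- Expected sample size at q = 0.25: 11 + 11 × P(X1≤1) = 11 + 11 × 0.19710 = **13.17**

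The stated 5%, 80% and 13.2 all reproduce.

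**2. The single count.** With X ~ Bin(22, q), P(X≤2) is:

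- q = 0.25: 0.001784 + 0.013081 + 0.045784 = **0.0606**
- q = 0.06: 0.25634 + 0.35996 + 0.24125 = **0.8576**

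The 5% does not reproduce. The 6.06% is an upper bound: a DSMB stop before 22 patients can only lower the chance of meeting the criterion. The smallest sample at which 2 or fewer alone holds 5% is 23 (4.92%, power 84.3%).

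**3. Source of the difference.** It is one outcome, X1 = 2 and X2 = 0:

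- q = 0.25: 0.25810 × 0.04224 = 0.0109 = 0.06065 − 0.04975
- q = 0.06: 0.11345 × 0.50630 = 0.0574 = 0.85755 − 0.80011

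**4. Upper confidence limits at 2 of 22,** solving P(success | q) = tail probability:

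| Rule | One-sided 95% | Two-sided 95% |
|---|---|---|
| Both limits | 24.98% | 28.2% |
| Single count | 25.95% | 29.2% |

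So a rate below 25% follows at the one-sided 5% level only under both limits.

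**5. How each text treats 2 SADE patients in the first 11 and 0 in the next 11.**

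| Text | Reading |
|---|---|
| Amended CIP synopsis (Study Design), 8.1.1, 9.1; SAP 2.5 | Success |
| Amended CIP 9.2 | Success by the count; its pointer to Table 7 is ambiguous |
| SAP 2.9 Table 2; SAP 7.2 | Failure |
| CIP 9.7; SAP 2.1, 2.10, 8.1 | Trial terminated; silent on the conclusion if all 22 were implanted |

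**6. Can it be observed?** Yes. Enrolment is consecutive, with DSMB discretion after a SADE. SAP 8.2 records the 11-patient DSMB review at one month, not three, and 21 patients past Visit 5 at the next analysis. Enrolment can therefore pass 11 before the first 11 have three months of follow-up.

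**7. Drop-outs.** With one stage-2 patient lost and the limits left at 1 and 2, X2 ~ Bin(10, 0.25): 0.04224 × 0.52559 + 0.15486 × 0.24403 = 0.0222 + 0.0378 = 6.0%. Fixed limits therefore cannot be written without the recalculation in SAP 5.2.

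**The case against.** **The addendum may have been superseded.** The SAP follows CIP Rev G of January 2016, while the CIP supplied is Rev C plus an addendum. This stands as a limit: the current CIP wording is unknown. It does not remove the difference between SAP 2.5 and SAP 2.9 and 7.2.

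**The single count may be shorthand.** SAP 2.5 speaks of a two-stage design, and SAP 2.1 puts the success criterion straight after the first-11 rule, so 2 of 22 can be read as the second half of a Simon rule. That is probably the intent, and on that reading the level is 4.97%. But a termination rule does not say how the final data are judged if enrolment ran on, and nowhere is it stated that it does.

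**Amended 9.2 points to Table 7,** which in Rev C shows both limits. True, but the addendum's replacement table drops the first-stage column, so the pointer is at best ambiguous.

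**The effect is small.** This stands. The excess is at most 1.1 percentage points, from one outcome, and only if the DSMB never stops enrolment.

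**Two stronger readings are tempting.** A reader might infer that the trial is, in fact, tested at 6.06%. The documents do not support that: the figure applies only if the disputed outcome counts as success, and several passages count it as failure. A reader might also note that, given exactly 2 SADE patients in 22, both fall in the first 11 in 55/231 = 23.8% of orders, and take this as the chance that the definition of the first 11 decides the result. It is not. If consent order and implantation order give the same 11 patients, the chance is zero; if they differ by one swapped patient, it is 20/231 = 8.7%. Nothing in the documents shows that the two orders differ.

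**Conclusion.** Wrong as written, and it should be fixed; the size does not make it critical. The 5% claimed in amended CIP 8.1.1, and the statement in amended 9.2 that the parameters are met, do not hold for 2 or fewer of 22 alone: type I error is up to 6.06%, with power 85.8%. The stated 5% and 80% belong to the rule with both limits (4.97%, 80.0%). The SAP leaves open which rule governs the conclusion, which matters for one outcome: probability 1.1% at a 25% SADE rate and 5.7% at 6%.

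This rests on a one-sided test, a null SADE rate of 25% (SADE-free proportion 0.75) and 22 evaluable patients. The binomial results are exact under those assumptions.

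**What to change.** **Main edit,** in SAP 2.1, 2.5 and 7.2 and the matching text of whichever CIP revision is current: safety is concluded at the 5% level only if at most 1 of the first 11 and at most 2 of all 22 patients have an SADE within 3 months, whether or not enrolment continued; if there are drop-outs after implantation, the critical values are recalculated under SAP 5.2.

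**Define the first 11 once,** consistent with the evaluable patients of CIP 9.2 and SAP 2.9. The SAP rule counts enrolled patients, CIP 8.3.4 and SAP 2.3 date enrolment from consent, CIP 8.3.3.2 says consented screen failures are not enrolled, and CIP 9.1 in Rev C counts implanted patients.

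**Correct amended 9.2** where it says the parameters are met by 2 or fewer in 22.

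**If the single count is kept instead,** state the level as 6.1%, use an exact single-stage interval (two-sided 95% upper limit 29.2% at 2 of 22) and declare that the choice was made after the looks recorded in SAP 8.2. Restating both limits would also come after those looks, but it is the stricter choice and both already stand in SAP Table 2.

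**Separately, reconcile two other pass criteria with 2 of 22.** The amended synopsis and 9.2 say "The study will be declared a success if the final non-safety event rate is less than 6" per cent, but 2/22 is 9.1%; taken literally only 1 of 22 (4.5%) passes, with alpha 1.5% and power 61.6%. CIP 9.5 requires fewer than two, counted over the follow-up period.

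**Stopping passages.** CIP 9.7, amended 8.3.3.1 and SAP 2.1, 2.10 and 8.1 contradict each other and must be reconciled by the sponsor.

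**Cost.** Wording only and no added patients, but the CIP part needs a formal amendment with ethics committee approval (CIP 12.3). Power is the planned 80% rather than 86%.

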9.2 Sample Size Calculation

The sample size calculation was based on the study's purpose of establishing safety.

To minimize the required sample size and consequently the number of patients exposed to risk while at the same time maximizing the chances of detecting safety events, a two-stage design based on the rate of non-events was chosen (Simon, 1989). The event of interest was defined as a serious device-related adverse events (SADEs). Based on a probability of non-events of $p_0=0.75$ for the first stage and an overall acceptable probability of $p_1=0.94$, a sample size of at least 11 evaluable patients in the first stage and additional 11 patients in the second stage are required. This maintains a type 1 error probability of 5% and the power of 80% based on minimizing the maximal sample size and results in an expected sample size of 13.2 patients.

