9.5 Pass/fail criteria to be applied to the results of the clinical investigation

This investigation will be considered a success if fewer than two of the total 22 patients (stage 1 and 2) experience SADEs during the follow-up period.

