2.1 Study Design

The trial will be conducted as an open, prospective, multicenter single-arm clinical trial following the principle of the two-stage design described by Simon (Simon, 1989) in patients with Primary Open Angles Glaucoma (POAG) and indicated cataract surgery. The purpose is to evaluate the safety of the ARGOS-IO system and to compare its performance to the Goldmann Applanation Tonometry (GAT).

All 22 patients will be enrolled consecutively, until a serious adverse device effect (SADE) occurs. In that case, the DSMB will be called, and decides whether the enrollment can be continued or not.

An interim analysis will be performed after half of the study population (11-14 subjects) is enrolled with a minimum follow-up of 1 month. Another interim analysis to assess Safety and Performance will be performed, when all patients have completed the 3 month follow-up visit, the 6 month follow-up visit and every time an SADE occurs.

In order to take the two-stage design described by Simon into account, the trial will be terminated, if more than 1 patient out of the first 11 patients enrolled experiences SADEs during the first 3 months of the post-surgical follow-up period.

A conclusion for safety will be made at the 5% significance level, if two or fewer of the total 22 patients experience an SADE. A corresponding 95% confidence interval for the SADE rate will be calculated according to the procedure of Koyoma (2008).

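### The success criterion for primary safety is stated in conflicting ways: exactly 2 of 22 patients with an SADE is both a pass and a fail, and only the two-or-fewer rule has the stated 80% power

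*Protocol*

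**What the plan says.** The success rule for the primary safety endpoint appears in three forms.

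- **Two or fewer of 22.** The amended Synopsis (Study Design) says "A conclusion for safety will be made if in total no more than 2 of the total of 22 patients experience an SADE". Amended CIP 8.1.1 and 9.1 agree. SAP 2.1 says "A conclusion for safety will be made at the 5% significance level, if two or fewer of the total 22 patients experience an SADE", and SAP 2.5 and Table 2 use the same count.
- **Final rate below 6%.** The amended Synopsis (Sample Size Considerations) and amended 9.2 say "The study will be declared a success if the final non-safety event rate is less than 6" per cent, and attach a type II error of 0.20. In amended 9.2 the paragraph then ends by saying that "those parameters will be fulfilled if 2 or less SADE will occur in a sample of 22 patients".
- **Fewer than two of 22.** CIP 9.5, the pass/fail section, says the investigation is "considered a success if fewer than two of the total 22 patients (stage 1 and 2) experience SADEs during the follow-up period". No visible part of the addendum changes it.

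The stated error rates are in CIP 9.3: "Significance level is set to 0.05, Power to 80" per cent. SAP 2.5 gives the test: "The specific hypothesis to be tested in this single arm two-stage design study is that the SADE rate is lower than 25" per cent.

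The event window differs too. CIP 7.1.1.1 and SAP 2.9, 6.2 and 7.2 use 3 months after implantation. CIP 9.5 uses the follow-up period, which CIP 8.3.6 puts at 12 months. The two-or-fewer sentences in the amended Synopsis, 8.1.1 and 9.1 give no window.

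**The concern.** The 6% figure is one minus p1, the SADE rate assumed under the planning alternative. The amended text uses it as a cut-off for the observed rate, which is a different and stricter rule than the one the sample size was built on. It then assigns that rule a type II error it does not have.

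If the trial ends with exactly two affected patients, the documents support both verdicts on the primary endpoint, and someone would have to choose after seeing the data. CIP 7.2 also makes the description of agreement with GAT conditional on the safety hypothesis being proven, so an ambiguous safety verdict carries over to the performance objective.

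**Working it through.** **Inputs.** n1 = 11 and n = 22 (CIP 9.2, SAP 2.9). SADE-free proportions p0 = 0.75 and p1 = 0.94, so SADE rates q = 0.25 (null) and q = 0.06 (alternative). Stage-1 stop if more than 1 of the first 11 has an SADE (CIP 9.7, SAP 2.10). No drop-out (CIP 9.4). Write b(n, x) = C(n, x) q^x (1 − q)^(n − x).

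**1. What each wording allows.** 1/22 = 4.5% and 2/22 = 9.1%. Below 6% means at most 1, and fewer than two also means at most 1. The three wordings therefore reduce to two rules: at most 2, or at most 1.

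**2. Reproduce the plan's figures (at most 2, with the stage-1 stop).**

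P(success) = b(11,0) × P(X2 ≤ 2) + b(11,1) × P(X2 ≤ 1), where X2 is the count in the second 11.

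- q = 0.25: b(11,0) = 0.0422, b(11,1) = 0.1549, b(11,2) = 0.2581. So P(X2 ≤ 1) = 0.1971 and P(X2 ≤ 2) = 0.4552. Type I error = 0.0422 × 0.4552 + 0.1549 × 0.1971 = 0.0497.
- q = 0.06: b(11,0) = 0.5063, b(11,1) = 0.3555, b(11,2) = 0.1135. So P(X2 ≤ 1) = 0.8618 and P(X2 ≤ 2) = 0.9752. Power = 0.5063 × 0.9752 + 0.3555 × 0.8618 = 0.800.
- Expected N under the null = 11 + 0.1971 × 11 = 13.17.

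These match the stated 5%, 80% and 13.2, so two or fewer with the stage-1 stop is the rule that was designed.

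**3. At most 1 of 22.** The stage-1 stop has no effect here, because a total of at most 1 already implies at most 1 in the first 11.

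- q = 0.06: 0.94^22 + 22 × 0.06 × 0.94^21 = 0.2563 + 0.3600 = 0.616. Type II error = 0.384.
- q = 0.25: 0.75^22 + 22 × 0.25 × 0.75^21 = 0.0018 + 0.0131 = 0.0149.

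**4. How often the verdicts differ at q = 0.06.** P(exactly 2 of 22) = 231 × 0.06² × 0.94^20 = 0.2413. Of this, both events fall in the first 11 with probability 0.1135 × 0.5063 = 0.0574, and those trials stop at stage 1. The remainder is 0.2413 − 0.0574 = 0.184, which equals the power gap 0.800 − 0.616.

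**5. Without the stage-1 stop** (a plain sequence of 22, as amended 9.1 reads), at most 2 has power 0.616 + 0.241 = 0.858. Its type I error is 0.0149 + 231 × 0.25² × 0.75^20 = 0.0149 + 0.0458 = 0.0606.

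| Rule | Power at 6% | Type I error at 25% |
|---|---|---|
| At most 2, stage-1 stop | 80.0% | 4.97% |
| At most 2, no stage-1 stop | 85.8% | 6.06% |
| At most 1, either way | 61.6% | 1.49% |

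**The case against.** The strongest reply is that the SAP already settles the test. It uses two or fewer of 22 and a 3-month window, and SAP 2.5 treats 6% as the expected rate, not the threshold being tested. This limits the practical harm. However, the SAP presents itself as an elaboration of the CIP. It neither withdraws CIP 9.5 or the 6% sentence nor mentions them under its changes in section 8.2.

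A second reply is that the SAP cites CIP Rev G, whereas the protocol available is Rev C with an addendum, and that 9.5 still uses two-stage language. Whether Rev G changed 9.5 cannot be checked. Even without 9.5, the conflict remains inside the single amended paragraph of 9.2.

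A third reply is that the 6% sentence refers to the true rate and is only badly worded. It speaks of the final event rate, which reads as an observed value. If the true rate were meant, 22 patients could not show it: with no SADE at all, the exact one-sided 95% upper limit is 1 − 0.05^(1/22) = 12.7%.

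A fourth reply is that the 80% and 5% do not belong to the amended design, which drops the fixed stage-1 stop from 8.1.1, 8.3.3.1 and 9.1. That is right as far as those sections go, and the 6.06% in the table shows the effect. CIP 9.7 and SAP 2.1, 2.10 and 8.1 keep the stop, so the 80.0% and 4.97% apply to the rule as the SAP will run it. Under either version, only the two-or-fewer rule reaches 80% power.

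**Conclusion.** The criterion is wrong as written. The documents give opposite verdicts at exactly two affected patients, an outcome with probability 18.4% at the design alternative (24.1% if the stage-1 stop is not applied). The type II error of 0.20 attached to the 6% sentence is incorrect: that rule has 0.38. Counting SADEs over 12 months instead of 3, as CIP 9.5 does, can only lower the chance of passing further.

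The figures assume 22 evaluable patients, independent outcomes, a common true SADE rate and no drop-out. Because this decides pass or fail on the primary safety endpoint, it must be corrected.

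**What to change.** Use one sentence throughout: safety is concluded if at most 2 of 22 patients have an SADE within 3 months of implantation, provided that no more than 1 of the first 11 did.

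- Delete the 6% success sentence and its type II error from the amended Synopsis and amended 9.2.
- Replace CIP 9.5 with the common sentence.
- Add the 3-month window and the stage-1 condition to the amended Synopsis, 8.1.1 and 9.1. The stated 5% depends on that condition.
- Describe 6% only as the SADE rate assumed under the alternative. CIP 7.2, and the sentences in SAP 2.5 and 7.2 that infer a rate of at most 6% from the confidence interval, need the same alignment.

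If the sponsor does intend an observed rate below 6%, state it as at most 1 of 22 everywhere, including the SAP, and restate power as 62% and type I error as 1.5%.

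The recommended correction is a matter of wording in the CIP, its addendum and the SAP. It needs no extra patients or data.
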